4 STUDY DESIGN

4.1 General Design

This is a non-inferiority, multi-center, randomized, active-controlled, single-blind, two-way crossover efficacy and safety in-patient study in subjects with Type 1 diabetes mellitus.

Subjects will be randomized to one of two treatment sequences below and will receive one dose within each treatment period separated by a washout period.

Table 1: Randomized Treatment Sequence

Treatment Sequence	Treatment 1	Treatment 2
1	G-Pen 1 mg	GlucaGen Hypokit 1 mg
2	GlucaGen Hypokit 1 mg	G-Pen 1 mg

In each period subjects will be confined to clinic at Day -1 before dosing, will undergo the following procedures and will be discharged at Day 1.

Day -1: Clinic arrival, assessments specified by protocol, evening meal in clinic.

Day 1:

- **Overnight monitoring (starting approximately at midnight) and Morning Procedures (starting at approximately 6 AM).**

Subjects will be monitored by glucose and will be given glucose and/or insulin to optimize plasma glucose levels. In the morning, plasma glucose (via YSI) will be assessed, and if > 270.0 mg/dL (> 15.0 mmol/L), the visit will be rescheduled after a minimum 3-day wait. Otherwise, the subject will be administered IV insulin to induce a baseline euglycemic steady state.

- **Baseline Euglycemic Steady State (early morning).**

Prior to starting the hypoglycemia induction procedure, the subject must have stable plasma glucose for at least 30 minutes at 95 ± 20 mg/dL (75 to 115 mg/dL [4.17 to 6.38 mmol/L]) at a stable IV insulin infusion rate varying no more than $\pm 20\%$ during which plasma glucose must be measured at least every 15 ± 2 minutes (i.e., at least 3 consecutive values in the target range at 0, 15, and 30 minutes).

The starting plasma glucose level (SG) will be determined as the average of the last 3 measurements taken over the final 30 minutes of the baseline euglycemic steady state period.

- **Hypoglycemia Induction Procedure (following baseline euglycemic steady state).**

Hypoglycemia will be induced by adding an initial IV bolus push dose of regular insulin diluted in normal saline until and further *insulin dose adjustments* specified in the protocol.

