5.3.6.3.7 Local Tolerability

Summaries for tolerability will be presented by treatment and tabulated by scheduled timepoints. Worst post-baseline cases or scores will be determined for each subject and analyzed, which will include all scheduled and unscheduled assessments, if any.

5.3.6.3.7.1 Injection Site Discomfort

The incidence of any injection site discomfort reported by the subject will be analysed descriptively with counts and percentages for all scheduled time points.

- None
- Any injection site discomfort (including 'Other');
- Pain;
- Itching;
- Tingling, twitching or numbness;
- Irritation.

The following descriptive statistics will be provided for all timing variables for subjects reporting at least one injection site discomfort:

- Counts and percentages of time of onset from study drug injection (0-<1 min, 1-2 mins, 3-5 mins, 6-9 mins, >=10 mins);
- Total duration of discomfort will be analysed with descriptive statistics for continuous variables.

5.3.6.3.7.2 Draize Scale (Erythema and Edema)

[figure not shown]
The incidence of erythema and edema will be analysed descriptively with counts and percentages by scheduled timepoints, worst post-baseline score, and by the categories indicated below:

Erythema Formation		Edema Formation	
Description	Score	Description	Score
No erythema	0	No edema	0
Erythema	1-4	Edema	1-4
Very slight erythema: Barely perceptible	1	Very slight edema: Barely perceptible	1
Well defined erythema	2	Well defined edema	2
Moderate erythema	3	Moderate edema: raised approx. 1mm	3
Severe erythema: Beet redness to slight eschar formation	4	Severe edema: raised more than 1mm and beyond exposure area	4

Subject will be counted only once per actual treatment and timepoint and once for worst post-baseline score or erythema/edema occurrence.

5.3.6.3.7.3 VAS

VAS is reported using a 100-mm scale.

VAS scores will be summarized by all timepoints and worst post-baseline score.

Mean VAS scores will be compared between the treatments. Comparison between the treatments will be performed using a mixed model with treatment, period and treatment*period as fixed factors and subject as a random factor. This analysis will be performed on the Safety population.

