6 STATISTICAL METHODS

6.1 General Considerations

The statistical analyses will be performed using SAS Version 9.4 (or higher). All tables, figures and listings will be produced in landscape format.

Data will be presented at each scheduled timepoint (nominal time), where applicable. However, time-related endpoints (time to event) will be summarized using actual time.

For actual time, two reference points will be used: (a) decision to dose and/or (b) injection of study drug, which are specified in the primary and secondary endpoint analyses.

The total number of subjects in the study group (N) under the stated population will be displayed in the header of summary tables.

All study data will be included in the study data listings. Listings will be displayed by subject in chronological order, if not stated otherwise.

For tabulated safety summaries, only the scheduled timepoints will be included in the summary tables. Unscheduled assessments will be listed and used for evaluation of worst post-baseline value in categorical assessments, where applicable.

Sample codes and calculations for the efficacy analysis are provided in Appendix 2: Code Fragments. Actual code or procedure usage can differ from these samples, based on the model and conditions that correspond to those pre-specified in the SAP. Additional analysis may be performed for the cases not specified in SAP and will be described in CSR.

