6.6.2 Pharmacodynamics Analyses

All PD parameters will be presented descriptively.

A mixed model with treatment, period and treatment*period as fixed factors and subject as a random factor will be applied to compare the least square mean differences. Log transformation will be applied if skewness is observed. Unstructured covariance matrix will be used for the covariance matrix unless the model failed. In such case, structured covariance matrix will be selected based on the one given the smallest AIC (Akaike Information).

P-value for the difference test and 95% confidence for non-inferior test will be reported.

Additionally, mean glucose curve from 0 to 180 minutes post receiving glucagon will be presented graphically for each treatment. For this group of figures, the protocol defined time will be used. The mean glucose curve during hypoglycemia induction time will also be presented for each treatment. Since there is no protocol time for hypoglycemia induction stage, the mean glucose will be summarized for every 5 minutes based on the glucagon injection time.

This will be conducted based on the mITT population only.

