APPENDIX 2: CODE FRAGMENTS

Risk difference test for binary response

```
Proc Freq data = <Data> order=data;  
    weight Count / ZEROS;  
    tables <Treatment>*<Response> / riskdiff;  
    output out = <Out> riskdiff;  
run;
```

Mixed model

```
ods output lsmeans(match_all) = <Out_LSmean>  
           Diffs(match_all) = <Out_Diffs>;  
Proc Mixed data=<Data>;  
    class <Treatment> <Period> <Subject>;  
    model <Value> = <Treatment> <Period> <Treatment>*<Period>;  
    random <Subject> / Type = un;  
    lsmeans <Treatment> / cl DIFF;  
run;
```

Time-to-Event

```
ods output means=<Out_Means> HomTests=<Out_Test>;  
proc lifetest data=<Data>;  
    time <Time>;  
    strata <Treatment>;  
run;
```

Study Drug Assignment

```
proc freq data=<Data>;  
    tables <Treatment>/ BINOMIAL (p=0.50) alpha=0.05;  
    output out=<Out> Binominal;  
    weight count;  
run;
```

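### The sample mixed-model code in SAP Appendix 2 puts an unstructured covariance on subject without blocking by subject; as printed it gives no usable fit for the PD and VAS comparisons

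*SAP*

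**What the plan says.** SAP 6.6.2 compares the PD parameters with a mixed model: treatment, period and their interaction fixed, subject random. On the covariance it says: "Unstructured covariance matrix will be used for the covariance matrix unless the model failed". If that model fails, a structured matrix is chosen by smallest AIC. No candidate structures are listed, and the text does not say whether the unstructured matrix runs over subjects or over periods within a subject.

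Appendix 2 gives the worked example. Its class line is "class <Treatment> <Period> <Subject>", its model line is "model <Value> = <Treatment> <Period> <Treatment>*<Period>", and its random line is "random <Subject> / Type = un". SUBJECT= appears nowhere in the fragment.

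The VAS comparison (SAP 5.3.6.3.7.3) names the same factors: "treatment, period and treatment*period as fixed factors and subject as a random factor. This analysis will be performed on the Safety population". It states neither an unstructured matrix nor an AIC rule.

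SAP 6.1 describes the status of the fragments: "Actual code or procedure usage can differ from these samples, based on the model and conditions that correspond to those pre-specified in the SAP".

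**The concern.** In PROC MIXED, a class variable on the RANDOM statement without SUBJECT= contributes one column per subject. TYPE=UN then asks for a separate variance for every subject and a separate covariance for every pair of subjects. A two-period crossover cannot estimate these. The matrix that makes sense is small and sits within each subject.

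The text of 6.6.2 does not settle what was meant. For a single random subject intercept, unstructured has no content, because there is only one variance. For a 2 × 2 matrix over periods, the random subject factor is redundant. A programmer has to guess, and the only example offered is the one that does not work.

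At stake are the p-values and 95% intervals that 6.6.2 promises for Cmax, Tmax and the two AUCs, and the VAS comparison. If the PD fit fails, the covariance structure is picked from the data out of an open set.

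**Working it through.** The plan states no figure on this point, so there is nothing to reproduce. SAS was not available; what follows concerns the model that the code requests, not an observed SAS log.

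**Inputs**
- Subjects: 122 randomized, 111 evaluable (SAP 4.2).
- Periods: two; each subject "will receive one dose within each treatment period separated by a washout period" (SAP 4.1). Each PD parameter therefore has one value per subject and period.
- Fixed effects: intercept, treatment, period, treatment-by-period (Appendix 2).

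**1. Parameter count as printed.** An unstructured q × q matrix has q(q+1)/2 parameters.
- q = 122: 122 × 123 / 2 = 7,503, plus 1 residual, against 2 × 122 = 244 values.
- q = 111: 111 × 112 / 2 = 6,216, plus 1 residual, against 2 × 111 = 222 values.
- VAS, assuming that all three times (30, 90 and 180 minutes) in both periods are modelled: 122 × 2 × 3 = 732 values, still against 7,503.

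**2. What a fit would do.** Split each complete pair into a sum and a difference. The differences depend only on the residual variance σ². The sums have covariance σ²I + 2G, where G is the subject matrix. Each part leaves n − 2 error contrasts.
- *G limited only to non-negative variances.* The REML likelihood has no maximum. In a simulated crossover with n = 20, −2 REML log-likelihood fell from 31.5 to −7.7, −46.8, −86.0 and −164.3 as the covariance was driven towards singular.
- *G forced to be positive semi-definite.* The best G has rank 1. It absorbs one direction of the sums, and the other n − 3 are counted as residual. The residual estimate becomes SS(differences)/(2n − 5) instead of SS(differences)/(n − 2), a ratio of (n − 2)/(2n − 5).
  - n = 122: 120/239 = 0.502; SE ratio √0.502 = 0.709.
  - n = 111: 109/217 = 0.502; SE ratio 0.709.
  - A nominal two-sided 5% test then has size 2[1 − Φ(1.96 × 0.709)] = 2[1 − Φ(1.389)] ≈ 0.165 (normal approximation).

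**3. The same fixed effects with the covariance blocked by subject.** A random intercept has 2 parameters (one between-subject variance, one residual). An unstructured 2 × 2 matrix over periods has 3. REML fits to simulated crossovers with n = 40 (a separate dataset for each row):

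| Data | Structure | Treatment difference | SE | AIC |
|---|---|---|---|---|
| All pairs complete | Random intercept | 0.23576 | 0.21244 | 124.03 |
| All pairs complete | Unstructured 2 × 2 | 0.23576 | 0.21244 | 125.64 |
| 4 second-period values missing | Random intercept | 0.53071 | 0.26558 | 125.37 |
| 4 second-period values missing | Unstructured 2 × 2 | 0.53515 | 0.26838 | 124.87 |

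Both structures can be fitted. With complete pairs they give the same treatment result. With 10% of second-period values missing, the SEs differ by 0.26838/0.26558 − 1 = 1.1%. The two are therefore not interchangeable, but the gap is small.

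**4. Whether incomplete pairs will occur.** SAP 4.2 anticipates 10% drop-out (122 − 111 = 11 subjects). The mITT population (SAP 5.1.2) requires only one dose. SAP 5.3.6.2.1 treats glucose as missing once insulin is restarted and leaves an AUC undefined when later values are missing. AUC to 180 minutes is the most exposed.

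**The case against.** The best defence is SAP 6.1: the fragments are samples, and the final code need only match the model in the text. That model, with treatment, period and interaction fixed and subject random, is standard and can be fitted. Once blocked by subject, an unstructured matrix needs three parameters. This stands. A reader might infer that the pre-specified model can never be used and that the PD and VAS analyses must always end in an AIC choice. The documents do not support that: it follows only if the code is run as printed, and for VAS there is no AIC rule at all.

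The second defence is that little would change. Fixed effects and the treatment contrast are pre-specified, so only the covariance could move. With complete pairs the treatment estimate is a within-subject difference and does not depend on the between-subject structure. Even an autoregressive structure across subject identifiers, which would have no meaning, left the estimates unchanged to four decimals in 12 simulated datasets of 40 subjects and moved the SEs by at most about 1%. The SAP does not say that such a structure would be tried, and dropping TYPE= would give ordinary variance components. This also stands for workable structures, but it does not cover the boundary solution of the printed code, where the estimate is unchanged and the SE is too small.

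What remains is that 6.1 ties the final code to the text, and the text leaves open which unstructured matrix is meant.

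**Conclusion.** The point holds as a coding and specification error of minor weight. As printed, the fragment asks for 7,503 covariance parameters from at most 244 PD values. It either fails or, under a positive semi-definite constraint with complete pairs, understates the treatment SE by about 29% (ratio 0.71), so that a nominal 5% test runs at about 16%. How SAS would report this was not observed.

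A failed PD fit would bring in the open AIC choice in 6.6.2. VAS would share the faulty code with no stated fallback. Among structures properly blocked by subject, the choice matters only for subjects with one period, and there only slightly in the simulation.

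The primary non-inferiority decision uses the risk difference (SAP 6.5) and is unaffected.

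**What to change.** 1. In Appendix 2, replace the RANDOM statement with `repeated <Period> / subject=<Subject> type=un;` for one value per period (3 parameters). Do not keep both statements: a random intercept plus this matrix would put 4 parameters on a 2 × 2 matrix with 3 distinct elements.
2. Name `random intercept / subject=<Subject>;` (2 parameters) as the single fallback if the first model does not converge. Say that it is a different model, with equal period variances.
3. In SAP 6.6.2, replace the AIC selection with that fixed order, and make the description of subject as a random factor agree with it.
4. Refer to the same order in SAP 5.3.6.3.7.3, and state which VAS value per period enters the model. If several times are modelled together, the covariance needs its own specification.

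The cost is a line or two of code and a few sentences of SAP text, with no change to data collection or sample size.
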